1.1 Background

Medical care of heart failure (HF) has been stagnant for the past 20 years; innovative therapy is urgently needed. A novel therapeutic target, mitochondrial dysfunction, has been implicated in multiple diseases, including heart failure. However, there currently is no specific treatment for mitochondrial dysfunction in human heart failure or any other disease. Mitochondria-based therapy development has been hampered both by limited understanding of how mitochondrial impairment causes cardiac dysfunction, and by a lack of interventions shown to improve mitochondrial function.

1.2 Study rationale

Recently, we demonstrated in a murine model, that impaired mitochondrial oxidative phosphorylation led to an increased myocardial NADH/NAD⁺ ratio and increased mitochondrial protein acetylation, without affecting mitochondrial ROS production or ATP synthesis. These changes rendered the heart susceptible to chronic stresses, which accelerated the development of heart failure. We observed a similar increase of NADH/NAD⁺ ratio and increase in protein acetylation in animal models of heart failure due to chronic pressure overload with no prior mitochondrial dysfunction. Supplying the NAD⁺ precursor, nicotinamide mononucleotide (NMN), to these mice normalized the NADH/NAD⁺ ratio, prevented increased mitochondrial protein acetylation and improved cardiac function. Though NMN is not orally bioavailable, we and others have shown that oral supplementation with nicotinamide riboside (NR), the precursor from which NMN is produced, also decreases (normalizes) tissue NADH/NAD⁺ ratio and improves mitochondrial function in mouse models. These animal model results suggest a conceptually innovative mechanism linking mitochondrial dysfunction to the development and progression of heart failure that is distinct from the existing hypotheses of oxidative stress and energy starvation. Thus, we hypothesize that oral supplementation with NR will increase NAD⁺ levels, thereby normalizing the NADH/NAD⁺ ratio caused by mitochondrial dysfunction during chronic stresses, and improve functional capacity and ventricular function in systolic heart failure.

We therefore propose a safety and tolerability trial of the nutritional supplement, nicotinamide riboside (NR) in 30 participants with clinically-stable, systolic heart failure.

1.3 Nicotinamide Riboside

NR is a relative of niacin, but a closer relative of nicotinamide which, unlike niacin, does not induce flushing or pruritis and has no effect on lipid levels. NR does not induce insulin resistance or dysglycemia in mouse models. Thus, NR would potentially be cheap, safe, well-tolerated and readily available. The application is in response to the program announcement of “Nutrition and Diet in the Causation, Prevention, and Management of Heart Failure” as NR has recently been approved for human use as a health supplement.

2. Study Objectives

The Study has three objectives: 1) to determine the safety and tolerability of NR in patients with clinically-stable, systolic heart failure (LVEF <40%); 2) to determine whether, at the doses employed, NR has measureable effects on whole blood NAD⁺ levels; and 3) to explore the potential range of effects of NR supplementation on heart failure surrogate endpoints.

3. Study design

3.1 Design Overview

This study is a single-center, prospective, double-blind, 2:1 randomization to NR or placebo, safety and tolerability trial of placebo versus nicotinamide riboside (NR) in participants with clinically stable (NYHA functional class I-IIIA) systolic heart failure (LVEF by echocardiography or radionuclide ventriculography <40%) due to non-ischemic or ischemic etiologies.

4. Study Population

4.1 Eligibility

4.1.1 Inclusion criteria

- Men and women aged 18 and older with systolic heart failure (LVEF by standard 2D echocardiography or radionuclide ventriculography of $\leq 40\%$) deemed, in the clinical opinion of their treating cardiologist to be non-ischemic or ischemic in origin.
- Clinically stable (no cardiac procedures or hospitalizations for hospitalizations for cardiac causes, including HF, ischemia or arrhythmia) within the previous 3 months
- Ability to undergo study procedures, including scheduled visits, blood draws and six-minute walk tests
- Willingness/ability to provide informed consent

4.1.2 Exclusion Criteria

- Heart failure with preserved ejection fraction (LVEF $>40\%$)
- Heart failure due, in the opinion of their treating cardiologist, to etiologies other than non-ischemic or ischemic. Examples of exclusionary heart failure etiologies include primary valvular disease, or infiltrative or inflammatory cardiomyopathies.
- Cardiac surgery, percutaneous coronary intervention (PCI) or cardiac device implantation within the previous 3 months
- Hospitalizations for cardiovascular causes, including heart failure, chest pain, stroke/TIA or arrhythmias within the previous 3 months
- Inability to perform Study visits or procedures (e.g., physical inability to perform 6MWT)
- Unwillingness/inability to provide informed consent
- ALT $> 3 \times$ upper limit of normal, hepatic insufficiency or active liver disease
- Recent history of acute gout
- Chronic renal insufficiency with creatinine $\geq 2.5 \text{ mg/dl}$
- Pregnant (or likely to become pregnant) women
- Significant co-morbidity likely to cause death in the 6 month follow-up period
- Significant active history of substance abuse within the previous 5 years
- Current participation in another long-term clinical trial
- History of intolerance to NR precursor compounds, including niacin or nicotinamide

4.2 Discontinuation of subjects from study treatment

This is a study of a nutritional supplement. For those participants taking nicotinamide riboside, a warm flushing sensation may occur when first taking this supplement. We will monitor for skin rash, increased blood sugar, or cause mildly abnormal hepatic function. In diabetic participants, it is possible that nicotinamide riboside may worsen glucose intolerance and necessitate an adjustment in medications for treatment of diabetes. We also will monitor for worsening in signs and symptoms of heart failure, by asking about worsening of dyspnea, dyspnea on exertion, orthopnea, paroxysmal nocturnal dyspnea, arrhythmia/palpitations or edema. We will monitor blood levels of B-type natriuretic peptide (BNP), serum electrolytes, BUN and creatinine at Study visits 1, 3, 4, 7 and visit 6 according to the PI's judgement.

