Potential study participants will be identified under HIPAA waiver by chart review. Their cardiologist will approve the approach before researcher contact. Potential participants will be contacted by phone using the approved phone script, or seen in person if at the clinic. Only if the participant expresses any interest will we continue study recruitment. To the participants who are interested in the study, study staff will explain the study's purpose and design and what would be required of participants. A series of questions will be asked to make sure the participant meets eligibility requirements. Then, the informed consent will be conducted by an investigator or a study coordinator. Participants will be encouraged to ask questions and to share the information with their regular doctor. A copy of this consent will be given to the participants; the original will be placed in the participant's study chart.

Protection Against Risks. All access to individually identified participant data is limited to the investigators who are directly involved in this research study, the clinical research staff of the Translational Research Unit during the subjects' visits, and the UWMC Research Testing Service. Study charts and password-protected databases are confidential and are not released to outside parties except at the participant's request. All blood samples for laboratory analysis outside UWMC are ONLY identified by a study number. The Study charts containing paper forms will be stored in the locked file cabinets in the research clinics or offices where they only can be accessed by the investigators. Each participant will receive a unique study number. The study number is linked to the participant's personally-identifiable information in the study database and used to perform data entry and linking.

Notification of Participants and Their Physicians. Study participants and their primary care or vascular care physicians will be notified if there is clinical worsening of their heart failure. We will leave the further clinical follow-up and treatment plans to be made by the participants' physicians. Participants will not be notified of the results of other laboratory studies performed specifically for this Study.

10. Potential Benefits of Research to the Participant and Others

Individual participants may benefit from this study by being on a nutritional supplement that has shown some promise in animal models of heart failure.

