11. Importance of the Knowledge to be Gained

If the Study can demonstrate that nicotinamide riboside is safe and well-tolerated in participants with systolic heart failure, this will form the basis of a follow-on study to assess the efficacy of nicotinamide ribose on surrogate endpoints in heart failure, such as functional capacity and ejection fraction. Thus, the Study may provide information necessary to further explore the clinical utility of this nutritional supplement in the treatment of systolic heart failure, a large and growing population of high risk participants for whom treatment, at present, is less than adequate.

12. Data Safety Monitoring Board

A Data Safety Monitoring Board (DSMB) will be instituted for this Study in order to ensure its ongoing safety and to oversee the Interim Analyses. Recommendation for trial continuation will be guided by monitoring boundaries at interim analyses at which formal efficacy analysis is performed as well as safety evaluations at all safety data reviews. Safety review meetings will be held by the DSMB prior to Study initiation, at which time the DSMB will develop any formal "stopping rule(s)" for the Study. The DSMB will meet three

additional times: after completion of 10, 20 and 30 Study participants. Safety data will include pre-specified evaluation of parameters for blood glucose, myopathy, hepatotoxicity, renal function as well as signs/symptoms of heart failure, or other possible clinical side effects such as gout, as requested by the DSMB. Enrollment to the study will continue throughout the scheduled meetings of the DSMB. The three-member, Study DSMB Roster is provided below.

- **[name].** (Chair)
Director, Clinical Trials Service Unit and Professor of Medicine (Cardiology)
University of Washington School of Medicine
- **[name]**
Professor of Medicine and Head, Division of Cardiology
University of Washington
- **[name]**
Deputy Director, Clinical Trials Service Unit and Assistant Professor of Medicine
(Cardiology)
University of Washington School of Medicine

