**NR in HF Study: Biostatistical Analysis Plan.**

**5.a. Statistical Methods.** After import into statistical software (R, Stata or SAS), data will be screened for outliers and the validity of any outlier values will be verified and/or any potential errors will be corrected. Changes in outcomes (including serum NR level, NADH/NAD+ ratio, 6MWT, MNQOL score, 3D-Echo, Doppler/TDI) from Week 0 to Week 12 will be compared between the NR and placebo arms using a two-sample t-test, the Mann-Whitney test or the permutation test, as appropriate. Changes in serum NR, NADH/NAD+ levels, 6MWT and MNQOL score outcomes over the multiple visits (0, 2, 4, 6, 8 and 12 Weeks) will be explored visually and by calculating and tabulating mean outcomes for each visit by assigned treatment.

Power calculations. Detectable differences for LVEF are calculated from power calculations for a two-sample t-test (PASS 2008, NCSS, Kaysville, UT), using the initial sample sizes of 20 patients in the NR group, 10 patients in the placebo group, and a dropout rate of 10%, leading to a final expected sample size of 18 and 9 patients in the NR and placebo groups, respectively. Two-sided tests, 0.05 significance level and 80% power are assumed. Based on these parameters we calculate a detectable difference of 1.190 standard deviations for a change in an outcome between the means in the placebo and NR groups. The standard deviation (SD) for the change in LVEF by 3D Echo is based on a study of 50 patients with LV dysfunction due to previous MI (32). The SD for change, measured between baseline and one year follow-up, was 7%, and scatterplots for the LVEF changes measured by MRI or 3D echo suggested that SD values for EF are similar for both modalities. We conservatively assumed that the SD at 12 weeks would not be smaller than that at 52 weeks.

Expected results. Assuming a 7% SD for LVEF change (32), the detectable difference by 3D-TTE for this 30 participant trial is 8.3%. Much larger sample sizes would be required to detect much lesser changes in LVEF. Thus, Study echocardiograms will explore the potential range of effect sizes for NR on LVEF.

|   |   |                   |
|---|---|-------------------|
| 
Table 1. Sample sizes to detect 5% or 3% differences in LVEF at 80%, 85% or 90% power (1:1 randomization and 2-sided <math>\alpha=0.05</math>). Total sample sizes are shown.
 | 
Sample Sizes (N) to Achieve Power of:
 |                   |

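### Treatment changes made after worsening are recorded, but no stated safety or outcome analysis counts them, so a glucose harm that is treated between Weeks 4 and 12 can be missed or diluted

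*Protocol*

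**What the plan says.** **Harm and response.** Protocol Section 4.2, repeated in Section 8, says of diabetic participants that "it is possible that nicotinamide riboside may worsen glucose intolerance and necessitate an adjustment in medications for treatment of diabetes". For heart failure, Section 9 (Notification of Participants and Their Physicians) says participants and their physicians "will be notified if there is clinical worsening of their heart failure", and then: "We will leave the further clinical follow-up and treatment plans to be made by the participants' physicians".

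**What is collected.** Sections 6.1.3 to 6.1.8 record adverse events and concomitant medications or interventions at Weeks 2, 4, 6, 8 and 12 and at the call 30 days after the final visit. Section 4.2 adds direct questioning on symptoms: "We also will monitor for worsening in signs and symptoms of heart failure, by asking about worsening of dyspnea". It schedules BNP, electrolytes and renal function "at Study visits 1, 3, 4, 7 and visit 6 according to the PI's judgement". The panels that contain glucose and HbA1c follow the same pattern: mandatory at screening and Weeks 2, 4 and 12, optional at Week 8.

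**What is analysed.** Section 12 describes the DSMB's material: "Safety data will include pre-specified evaluation of parameters for blood glucose, myopathy, hepatotoxicity, renal function as well as signs/symptoms of heart failure", plus other possible clinical side effects that the board requests. Treatment changes are not named. The SAP has one between-arm test, in which changes in serum NR, NADH/NAD⁺, "6MWT, MNQOL score, 3D-Echo, Doppler/TDI) from Week 0 to Week 12 will be compared between the NR and placebo arms". It gives no rule for treatment started or increased after randomization, and no analysis of adverse events, safety laboratory values or concomitant medication.

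**The concern.** The first objective is safety and tolerability. For glucose, the protocol itself foresees a sequence of harm followed by a drug change. Once the drug change takes effect, the laboratory value no longer shows the harm that prompted it, and the clearest remaining trace is an entry in the medication log. That entry is not part of any stated safety measure. Nothing in Sections 6.1.3 to 6.1.8 makes an increase in diabetes medication an adverse event, so it can stay in the log uncounted.

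The same applies more weakly to heart failure. If therapy is intensified after worsening, later BNP, 6MWT, MNQOL or LVEF values describe the participant on that added therapy. At stake is whether the trial can report the risks it names without a bias toward no difference.

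**Working it through.** **1. Which stated safety measures would register each kind of treated harm**

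| Source of information | Heart failure | Glucose |
|---|---|---|
| Direct symptom questions (4.2) | Yes | None stated |
| Named for the DSMB (12) | Signs and symptoms | Laboratory parameters only |
| Mandatory laboratory tests after randomization | Weeks 2, 4, 12 | Weeks 2, 4, 12 |
| Adverse-event record | If reported as one | If reported as one |
| Medication record | Taken, no stated use | Taken, no stated use |

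The heart-failure risk has a second stated channel, symptoms. The glucose risk does not.

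**2. The unobserved interval.** The mandatory draws fall on Day 28 ± 3 and Day 84 ± 5. The nominal gap is 84 − 28 = 56 days of an 84-day treatment period, or two thirds. With the windows it runs from 79 − 31 = 48 to 89 − 25 = 64 days. By the dispensing lists in Sections 6.1.2 and 6.1.3, the Week 4 draw comes after about one week on the highest dispensed dose, so most exposure at that level falls inside this gap.

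**3. The plan's own figure.** For a two-sample t-test with n = 18 and 9, df = 25 and noncentrality d × √(18 × 9/27) = d × √6, 80% power at two-sided 0.05 gives d = 1.1901. The SAP states 1.190. Multiplied by the 7% SD this is 8.33%, against 8.3% in the SAP. The figure reproduces. It assumes no dilution by added treatment.

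**4. Dilution, as an illustration.** Let m be the share of the arm-level mean harm that added treatment has reversed by Week 12. Then observed difference = true difference × (1 − m). The documents give no value for m, so a range is shown for a true difference of 1.190 SD at 18 versus 9.

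| m (assumed) | Observed difference (SD) | Power |
|---|---|---|
| 0 | 1.190 | 80% |
| 0.10 | 1.071 | 71% |
| 0.25 | 0.893 | 56% |
| 0.50 | 0.595 | 29% |
| 0.75 | 0.298 | 11% |
| 1.00 | 0 | 5% |

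The sign reverses only if m exceeds 1.

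**5. Scale of the LVEF effect.** Suppose 2 of 18 NR participants gained 5 points from added therapy (assumed). The arm mean would shift by 2 × 5/18 = 0.56 points. The standard error of the contrast is 7 × √(1/18 + 1/9) = 2.86 points, so the shift is about 0.2 standard errors and about 7% of the 8.3-point detectable difference.

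**6. What a count could show.** At 20 versus 10, with assumed true event rates of 50% and 10%, Fisher's exact test has about 54% power. With 30% and 10% it has about 10%. The count is descriptive.

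**The case against.** The strongest reply is that safety in this trial is much more than laboratory parameters and Week 12 values. A reader might infer otherwise from Section 12 and the SAP, but the documents do not support it: adverse events are taken at six contacts, heart-failure symptoms are asked about, laboratory tests are also drawn at Weeks 2 and 4, and the DSMB may request other side-effect data. A worsening that led to treatment could surface through any of these. This stands, and it largely covers the heart-failure half. It does not close the glucose half, where the only named measure is laboratory-based. What the DSMB may ask for is discretion, not a plan.

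Second, the SAP's named Week 12 outcomes do not include glucose, HbA1c or BNP. The list is open-ended, but it is not a stated glucose analysis that is biased. This also stands. The SAP states no safety analysis at all, and the present point is one part of that wider absence.

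Third, the glucose route is narrow. Section 6 blinds participants to study laboratory results, and Section 9 has physicians told only of clinical heart-failure worsening. No stated route leads from a study glucose value to a drug change, so it would have to come from outside information. That makes m near 1 hard to argue. It also means that such a change would appear mainly in the medication record, which is the record left unused.

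Fourth, comparing everyone as randomized whatever treatment followed is a legitimate choice and fits Section 6.1.2, which keeps every randomized participant in the study. Agreed; that comparison should stay.

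**Conclusion.** The point holds in a limited form. The protocol foresees a change of diabetes medication after an NR-related glucose harm, permits treatment changes after heart-failure worsening, and records both, but neither Section 12 nor the SAP says that they are counted. For glucose, a harm that arises and is treated in the roughly 56 days between mandatory draws can be missed or diluted. For heart failure the gap is smaller, because symptoms are asked about and reach the DSMB.

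The size cannot be stated, because the documents give no rate of diabetes, of treatment change or of reversal. The power figures under the dilution check show only how sensitive a diluted contrast would be under assumed values of m.

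Two further inferences are not supported. One is that heart-failure treatment changes are expected: Section 9 only leaves them to the physicians. The other is that a treated harm would look like benefit. That needs treatment to more than offset the harm on average, for which the documents give no evidence, and the LVEF example is trivial beside 8.3 points.

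**What to change.** In Section 12 and the SAP:

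- Define a glucose safety event as the pre-specified laboratory rise or any start or increase of glucose-lowering treatment after randomization.
- Define a worsening-heart-failure event so that it includes any start or increase of heart-failure treatment given for worsening.
- Tabulate both by arm for the DSMB and the final report, glucose also by baseline diabetes, beside adverse events and laboratory changes. Label them descriptive.
- Flag these participants in the Week 12 outcome listings, and keep the as-randomized comparison.

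Separately, reconcile Sections 4.2, 6 (laboratory results) and 9 on how a diabetes medication adjustment would arise while participants are blinded to study laboratory results.

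The cost is wording in the SAP and the DSMB report. Concomitant medications are already recorded, and Section 6.1.2 updates current treatments at randomization, which gives the reference point. The documents do not show the fields of the medication form, so check that it holds dose, date and reason for change. The change concerns counting only and leaves patient care as it is. The downside is that some drug changes unrelated to worsening will be counted, in both arms, and that at 20 versus 10 the counts will not support a formal conclusion.

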4.3 Subject identification

Each subject will receive a unique study ID. Once assigned to a subject, the subject's ID will not be re-used.

5. Treatments

Participants will be randomized to either NR at an initial dose of 250mg tablets or placebo two times per day. The NR dose then will be up-titrated weekly by 250mg/dose to a final dose of 1000mg two times per day at the end of Week 4. Participants will be continued on the 1000mg two times per day dose up to the final follow up visit (week 12). If, at any step, a dose increase is not tolerated, the maximum previously-tolerated dose will be continued through to week 12.

6. Procedures

Every attempt should be made to complete the follow-up visits during the defined window periods. A final follow-up visit is required for all participants. In the rare cases a final follow-up visit cannot occur within the 5-day timeframe following study end date, any attempt to contact must be recorded on a special contact form, until/unless appropriate information is obtained.

[figure not shown]
Laboratory results:

Participants will be blinded to the results of laboratory studies obtained as a part of this Study.

Echocardiography results:

Participants will be blinded to the results of echocardiograms obtained as a part of this Study.

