6.1.3 Follow-up visit 3 (week 2)

The following procedures will be performed at the follow-up visits (Day 14±3):

- Update as needed demographic information, medical history, current medical treatments
- Vital signs and weight
- MNQOL score
- Fasting blood draw: ONE 5mL pearl top tube (for BNP), TWO 3mL lavender top tubes (for CBC, HbA1C); ONE 4mL lime top tube [for uric acid, ALT, CK, Chemistry panel (electrolytes, glucose, blood urea nitrogen and creatinine)], ONE 4mL gold SST tube (for insulin), and ONE 2.7 mL “blue top” tube for whole blood NR and NAD+ levels
- 6MWT
- Record of adverse events, if any
- Study drug adherence
- Record of concomitant medications or interventions, if any
- Dispense blinded study medication:
 - 750mg PO BID or Placebo for one week
 - 1000mg PO BID or placebo for one week

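### Participants are told no study laboratory results, with no exception for clinically significant safety values, and the only written trigger for notifying them or their physicians is clinical heart-failure worsening

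*Protocol*

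**What the plan says.** Protocol Section 6, under Laboratory results, reads: "Participants will be blinded to the results of laboratory studies obtained as a part of this Study". Section 9, in the paragraph on notifying participants and physicians, repeats it: "Participants will not be notified of the results of other laboratory studies performed specifically for this Study". The same paragraph gives the single trigger for contact: participants and their primary care or vascular physicians "will be notified if there is clinical worsening of their heart failure". It then assigns what follows to those physicians: "We will leave the further clinical follow-up and treatment plans to be made by" them.

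Section 4.2, largely repeated in Section 8, lists what the team will watch for, including raised blood sugar and mildly abnormal hepatic function. It adds that in diabetic participants NR could "necessitate an adjustment in medications for treatment of diabetes". BNP, electrolytes, BUN and creatinine are checked "at Study visits 1, 3, 4, 7 and visit 6 according to the PI's judgement".

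The Week 2 visit (Section 6.1.3) includes a full safety draw. It also dispenses a week of 750 mg BID, followed by "1000mg PO BID or placebo for one week". Section 12 has the DSMB review glucose, muscle, liver and kidney parameters after 10, 20 and 30 participants have completed.

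The SAP does not address the matter.

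**The concern.** This is a safety and tolerability trial with weekly forced up-titration in people with systolic heart failure. The protocol names a laboratory-detectable effect, worsening glucose control, that may require a prescriber to change treatment. It then leaves treatment with physicians whom it does not undertake to inform of that result, and it prevents the participant from learning of it.

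Read literally, a diabetic participant whose glucose climbs during escalation, without any change in heart-failure status, meets no notification trigger. Whether the prescriber hears depends on discretion that is not written down: no alert limit, no time frame and no responsible role. The issue is participant protection and clarity of procedure. It does not bear on the validity of the planned comparisons.

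**Working it through.** The plan states no figure on this point, so the check is mainly a reading of the relevant sections side by side.

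**1. Is there an exception to the rule?** The Section 6 sentence has no qualifier. In Section 9 the word *other* may leave room to disclose results connected with heart-failure worsening. It opens nothing for glucose, liver or muscle values that are abnormal for another reason.

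**2. Which results are anticipated or reviewed, and what step is written for each?** All are drawn at Visits 1, 3, 4 and 7, and optionally at Visit 6.

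| Result | Where the Protocol raises it | Written step to the physician | Participant |
|---|---|---|---|
| Glucose, HbA1c | Sections 4.2 and 8 (raised glucose, possible diabetes-treatment change); Section 12 (glucose) | None | Not told |
| ALT | Sections 4.2 and 8 (mild hepatic abnormality); Section 12 (hepatotoxicity) | None | Not told |
| CK | Section 12 (myopathy) | None | Not told |
| Creatinine, electrolytes | Section 4.2 (monitored, listed just after heart-failure symptoms); Section 12 (renal function) | None, unless heart failure has clinically worsened | Not told, unless *other* is read to allow it when heart failure has worsened |

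**3. Does another provision supply the missing step?**
- Section 4.2 is headed as dealing with discontinuation, but it gives no laboratory threshold for stopping or for reporting.
- Section 5 holds the last tolerated dose if an increase is not tolerated, but does not say whether a laboratory value can count as intolerance.
- The Week 8 draw (Section 6.1.6) is available when there is a safety concern, but no reporting step is attached to it.
- The DSMB (Section 12) reviews data at three points defined by completed participants, and any stopping rules it develops are for the study. Neither is notification of an individual.

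**4. Where does timing matter most?** The Week 2 draw falls on nominal Day 14, at the end of the week on 500 mg BID. The supply dispensed at that visit moves the NR arm to 750 mg BID and, 7 days later, to 1000 mg BID.
- Dose ratio from the Week 2 draw to target: 1000 / 500 = 2.0, that is, 1000 to 2000 mg per day.
- Next scheduled contact (Visit 4): 28 − 14 = 14 days later. With the ±3-day windows the range is (28 − 3) − (14 + 3) = 8 to (28 + 3) − (14 − 3) = 20 days.

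So the dose doubles before the next scheduled contact. These figures place the dose steps relative to the draw. They do not estimate how long the investigator would take to act, and the doubling applies only to NR participants (20 of the planned 30).

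**The case against.** The strongest reply is that the rule binds what participants are told and nothing else. The investigator is not blinded to safety values: bloods at Visit 6 are left to the PI's judgement, which presupposes that someone reads the earlier ones. Foreseeing an adjustment of diabetes medication likewise presupposes that someone acts on glucose. Keeping participants unaware of results is also a reasonable choice in a double-blind trial with a walk test and a questionnaire among its outcomes. All of this stands. It narrows the point to an unwritten route to the physician and a written bar on telling the participant.

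It can also be said that limits may exist in DSMB material, in the consent pages or in the Section 6 figure, none of which was available. That is possible. But the unqualified sentences in Sections 6 and 9 would then conflict with those limits and would still need the exception.

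Several stronger readings are tempting, and the documents do not support them:
- *That physicians may not be told.* Nothing says so. The line in Section 9 that study charts and databases "are confidential and are not released to outside parties except at the participant's request" concerns release of records. The next paragraph commits the team to contacting those same physicians about heart-failure worsening.
- *That serious liver or kidney injury is expected.* The protocol speaks of mildly abnormal hepatic function, and it lists creatinine alongside heart-failure monitoring. Glucose is the only effect for which it foresees a change in treatment.
- *That participants go unwatched between the mandatory Week 4 and Week 12 draws.* There is a telephone visit at Week 6 and an in-person visit at Week 8, with a draw available for safety concerns. Draw frequency is in any case a separate matter, and the fix does not change it.
- *That every withheld laboratory set is a missed warning.* Most sets may be normal. The documents give no rate of abnormal values.

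**Conclusion.** The concern holds in a limited form. Two sections state, without exception, that participants do not learn their study laboratory results, and notification of anyone is tied to clinical heart-failure worsening alone. A laboratory-detected problem of the kind the protocol anticipates, glucose above all, therefore has no written route to the prescriber and is barred from reaching the participant.

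The size cannot be expressed as a number of affected participants. What can be said is that the gap covers every on-study safety draw in principle, and that it is most consequential at Week 2, when the dose is about to double. The conclusion assumes that the supplied text is the operative rule, and it does not assume that the investigator would fail to act. The change should be made because it protects participants cheaply. No analysis or sample-size result depends on it.

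**What to change.** Add the following to the blinding sentence in Section 6 and the non-notification sentence in Section 9: *except that clinically significant safety-laboratory abnormalities (glucose/HbA1c, ALT, CK, creatinine, electrolytes) crossing an alert limit agreed with the DSMB before initiation will be reported promptly by the investigator to the treating physician, and to the participant where action is needed.*

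Set the limits at the DSMB's pre-initiation meeting. The exclusion criteria in Section 4.1.2 offer starting points: ALT above 3 times the upper limit of normal, and creatinine of 2.5 mg/dl or more. Creatinine also needs a change-from-baseline limit, because anyone entering below 2.5 / 2 = 1.25 mg/dl could double and still not reach 2.5.

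Require Week 2 results to be reviewed before the 1000 mg BID step. This assumes that results return within the intervening week; the documents give no turnaround time. The 750 mg BID step, dispensed at the same visit, may begin sooner, and the fix accepts that. State also that crossing an alert limit can count as intolerance under the Section 5 dose rule.

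NR, NAD+, insulin, mitochondrial-function and echocardiogram results stay blinded, and BNP need not be disclosed to participants.

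The cost is one clause in two places, a short list of limits and an instruction for reporting. No visits or draws are added. The downside is a small chance that a disclosed value hints at the assigned arm. Reporting to the physician first, and to the participant only where action is needed, keeps that chance low.
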